An Initial Feasibility Study of Brief Cognitive Behavioral Therapy for Suicidal Inpatients

Rationale. Suicide is a major public health problem: suicidal ideation affects 14% of the adult U.S. population, and as many as 5% have a lifetime history of suicide attempts.¹ Among individuals with depressive disorders, there is an 11% mortality rate from suicide.²

Although inpatient treatment provides immediate stabilization and crisis management, the risk of suicide post-discharge is substantial. Approximately one third of all suicides by individuals with mental disorders occur in the 90 days following hospitalization.³ A review of nearly 2 million adult psychiatric inpatients found that the suicide rate in the 90 days after discharge for patients diagnosed with depressive disorders was 235.1 per 100,000 person-years, markedly higher than that in the US general population (14.2 per 100,000 person-years).⁴

Cognitive behavioral therapy (CBT) has been shown to reduce both suicidal ideation and behavior.⁵⁻⁸ Though specific protocols vary, typical interventions include problem-solving training,⁹ cognitive restructuring,¹⁰ and training in emotion regulation skills.¹¹ To date, most of the existing research on CBT has been in outpatient samples, and the efficacy of inpatient CBT for suicide prevention is not clear.

Project Aims. The aims of the proposed project are to:

1. develop and implement a brief CBT for suicide prevention on the adult inpatient units;
2. conduct a brief feasibility test and collect initial pilot data on efficacy; and
3. collect preliminary data on the effects of CBT on implicit cognitive suicide associations.

Method. We selected [name] *et al.*'s¹² CBT protocol for the proposed project. This protocol was tested in a randomized controlled trial (RCT) of outpatients and resulted in a significant reduction in suicide attempts over a 24-month follow-up assessment (hazard ratio = 0.38); those receiving CBT were 60% less likely to make a suicide attempt than were those receiving treatment as usual.¹³ Of the 6 RCTs that measured suicidal behavior, this was the strongest behavioral effect documented.⁷

There will be two phases involved in this project, which are described below:

In Phase 1 of the project, we will work with [name] to modify his treatment protocol for use in an inpatient setting, and attend a two-day training in the protocol from [name].

In Phase 2 of the project, we will conduct an initial feasibility trial with 5-10 inpatients.

Participants. We will recruit 5-10 consecutive adult inpatients (dependent on flow within the 6-month treatment window) from the Donnelly units. Inclusion criteria will be:

1. males and females
2. age 18-65 inclusive
3. fluent in English (speaking, reading, and writing)
4. having made a suicide attempt within one week preceding admission. Admission will be defined as admission to either Harford Hospital medical floor (in cases where medical stabilization is required prior to transfer to IOL) or to IOL (in cases where medical stabilization is not required). A suicide attempt will be defined as behavior that is self-directed and deliberately results in injury or the potential for injury to oneself for which there is evidence, whether explicit or implicit, of intent to die.

Exclusion criteria will be:

1. age <18 or ≥66 years old
2. history of schizophrenia spectrum disorder
3. history of mental retardation or organic brain illness
4. current substance use disorder

5. active mania or other psychiatric or medical condition that would preclude informed consent or participation in the trial, in the investigator’s opinion
6. ECT included on patient’s inpatient treatment plan. Patients who are referred for ECT after starting the study will be withdrawn from the study.

Measures. Participants will complete a brief self-report demographic form. Diagnostic status will be measured at pre-treatment using the Diagnostic Interview for Anxiety, Mood, and Obsessive-Compulsive and Related Disorders (DIAMOND).¹⁴ Suicidal ideation and behavior will be assessed using the Columbia-Suicide Severity Rating Scale (C-SSRS).¹⁵ The C-SSRS can be scored to yield an ideation severity score (range 0-5) and a behavior severity score (0-5); suicidal behavior can also be scored dichotomously (present/absent). The C-SSRS will be administered with the timeframe for the “past week” at admission (i.e., pretreatment), and “since admission” at posttreatment, and “past week” at follow-up assessments. Depressive symptoms will be measured using the Structured Interview Guidelines for the Hamilton Rating Scale for Depression (SIGH-D),¹⁶ a well-validated clinician-rated interview for depression. Treatment acceptability will be measured using the Client Satisfaction Questionnaire (CSQ),¹⁷ an 8-item self-report measure.

At pre-treatment and post-treatment, we will also administer an *Implicit Association Test* (IAT).¹⁸ The IAT is a brief computer-administered test that uses people’s reaction times when classifying semantic stimuli to measure the automatic mental associations they hold about various topics, in this case, life and death/suicide. Participants classify stimuli representing the constructs of “death” (i.e., die, dead, deceased, lifeless, and suicide) and “life” (i.e., alive, survive, live, thrive, and breathing) and the attributes of “me” (i.e., I, myself, my, mine, and self) and “not me” (i.e., they, them, their, theirs, and other). Response latencies for all trials are recorded. The relative strength of each participant’s association between “death” and “me” is indexed by calculating a *D* score for each participant; positive *D* scores represent a stronger association between death and self (i.e., faster responding on the “death”/“me” blocks relative to the “life”/“me” blocks), and negative scores represent a stronger association between life and self.

Procedures. It is anticipated that the treatment component of the study will take place over a period of six months.

Participants will be recruited by a member of the research staff on the day following their inpatient admission or later (for example in the case of a Saturday admission). Patients who meet all of the inclusion criteria and none of the exclusion criteria and agree to participate will provide written informed consent prior to any study procedures. Informed consent will be documented using the Documentation of Informed Consent Form. For patients who are admitted to the hospital involuntarily documentation of competency to provide consent will be completed as well. Only those involuntarily committed patients who have been found competent to provide informed consent for research will be consented. Patients who decline participation will not be approached again. Patients who agree to participation will undergo the informed consent process. This process will involve providing the patient with the informed consent and HIPAA authorization forms to read. The study staff member obtaining consent will highlight the voluntary nature of the research and emphasize that the patient’s decision whether or not to participate will not impact his “usual care” treatment plan; however, patients will also be informed that the information discussed with the study clinician is shared with the inpatient treatment team, and thus may be used by them when making decisions about discharge planning. Patients will be informed that they may keep the forms to review with others if they wish to do so before signing. In addition, all questions the patient has about study participation will be answered prior to obtaining written consent.

Enrolled participants will undergo a clinical assessment by an independent evaluator (IE), who will administer the DIAMOND, C-SSRS, SIGH-D, and IAT.

Participants will receive up to 10 daily sessions of CBT (depending on length of stay), lasting 1.5 hours for the first session and 1 hour for the remaining sessions, following the manualized protocol developed in Phase 1. The CBT protocol is designed to be delivered in two phases. In phase I, the therapist conducts a detailed assessment of the

patient’s most recent suicidal episode or suicide attempt, identifies patient-specific factors that contribute to and maintain suicidal behaviors, provides a cognitive behavioral conceptualization, collaboratively develops a crisis response plan. The crisis response plan is reviewed and updated in each session by adding new skills and/or removing skills determined to be ineffective, impractical, or too challenging. In phase II, the therapist teaches the patient new coping skills inclusion emotion regulation strategies (e.g., relaxation, mindfulness) and cognitive strategies to reduce beliefs and assumptions that serve as vulnerabilities to suicidal behavior (e.g., hopelessness, perceived burdensomeness, guilt and shame). During the first session of CBT, participants are provided with a small pocket-sized notebook (called a “smart book”) in which they are directed to record a “lesson learned” at the conclusion of each session. Lessons learned include new skills learned or knowledge gained by participants during each session. Participants are encouraged to use the smart book in the future as a memory aid for managing emotional distress and solving problems.

Data Storage and Security. Audiotapes will be made of each session. All CBT sessions will be audiotaped using digital recorders. Audio files will be stored electronically with password-access login maintained on the HHC server. Access to the audiofiles will be limited to IRB-approved study staff. Files will be maintained for 6 years following studying closure at which time they will be permanently deleted. A psychologist trained in the CBT protocol will review audiotapes of all sessions and will rate treatment fidelity according to a checklist developed in collaboration with [name]. Deidentified excerpts from audiorecordings may be transcribed for inclusion in research publications.

Participants will then meet with the IE again for the C-SSRS, SIGH-D, IAT, and CSQ after the 10th session or within 24 hrs. prior to discharge, whichever comes first. After discharge, participants will have a telephone interview at 1 month, 2 month, and 3 month follow-up. The IE will administer the C-SSRS during these calls. Chart review (via Epic) will also be completed on study eligible participants (whether or not recruited). Data retrieved at 1, 2, and 3-month post-discharge will include readmission rates to the IOL or ED. Whether suicide attempt preceded admission will also be recorded. Demographic and clinical information will also be collected from the medical record (age when < or = 89, sex, race/ethnicity, diagnoses, medication, length of stay, suicide method) to compare study eligible participants who were versus were not recruited to determine if the groups were matched on these variables. At least three telephone calls will be made to try to reach a participant to complete the follow-up assessments. If a participant is unable to be reached by phone for the follow-up assessment after three tries then a letter will be sent to the participant asking them to contact the IE to inform her whether or not they wish to continue in the study. If a participant fails to contact the IE within 1 week of the study team sending the letter then a second letter will be sent again requesting that the participant contact the IE to let her know whether or not they wish to continue in the study along with a date by which the participant should contact the IE. If the participant does not contact the IE by the date stated in the letter they will be withdrawn from the study.

Adverse Event reporting.

Any severe adverse events (SAEs) that occur will be reported to the HHC IRB in a timely fashion, according to policy 901. Unexpected Severe AE’s – those rated 3-5 – will be reported within 7 calendar days of learning of the event.

Analytic Plan. It is noted that this is an initial test of feasibility and is therefore not powered for statistical significance. Though we will conduct significance tests, of greater importance are the following outcomes (all analyses will be intent-to-treat):

1. Mean CSQ scores at post-treatment, indicating acceptability of treatment.
2. Percent attrition rate, indicating acceptability of treatment.
3. Mean treatment fidelity rating, indicating our capacity to administer the treatment as described.
4. Effect size (Hedges’s *g*) of IAT D scores from pre- to post-treatment

5. Effect size (Hedges’s *g*) of C-SSRS ideation severity score from pre-treatment through follow-up
6. Effect size (Hedges’s *g*) of C-SSRS behavior severity score from pre-treatment through follow-up
7. Effect size (Hedges’s *g*) of SIGH-D score from pre-treatment through follow-up
8. Effect size (Hedge’s *g*) comparing study enrolled versus study eligible (but not recruited) participants on readmission over the follow-up.

Future Plans. The proposed study will yield feasibility and initial efficacy data that will be used to inform a grant proposal to the American Foundation for Suicide Prevention. That proposal will fund a randomized controlled trial of CBT vs. treatment as usual. Concurrently, we will develop an in-house program to train other staff in the protocol, and will submit a second grant to investigate the efficacy of the training program as well as the efficacy of CBT by those clinicians (benchmarking analysis).

Budget and Budget Justification

[name]. (Principal Investigator, 5% time, no salary requested): [name] will be responsible for overseeing all aspects of the proposed study. He will participate in weekly supervision with the therapist and with consultant [name]. [name] will conduct the outcome analyses and will bear responsibility for publishing the results of the study. [name] will donate his time to the study.

[name]. (Consultant): [name] is a leading expert in CBT for suicide prevention, the author of the treatment protocol used in the proposed study, and was principal investigator on an RCT of that protocol. His involvement is critical for ensuring adequate application of the treatment. [name] will provide a 2-day training for the clinical staff (\$11,000 for his fees plus travel expenses). Following that training, he will participate via videoconference in weekly group supervision meetings during the treatment phase of the study (\$200 x 16 meetings = \$3200).

[name]. (Project Manager, 10% time and salary): [name] will supervise the research assistant and coordinate the day-to-day operations of the study. She will participate in the weekly supervision meetings. She will also listen to audio recordings of at least 10% of all sessions to rate treatment fidelity.

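### The C-SSRS windows have inconsistent anchors: depending on the reading, baseline can miss the qualifying attempt or the post-treatment score can include days before CBT

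*Combined protocol and SAP*

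**What the plan says.** In the combined protocol and SAP, four statements fix the timing.

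- **Eligibility (Participants, inclusion criterion 4).** The patient must qualify by "having made a suicide attempt within one week preceding admission". The anchor is then defined: "Admission will be defined as admission to either Harford Hospital medical floor (in cases where medical stabilization is required prior to transfer to IOL"), and otherwise admission to IOL.
- **Baseline window (Measures).** "The C-SSRS will be administered with the timeframe for the “past week” at admission (i.e., pretreatment").
- **Later windows (Measures, same sentence).** "and “since admission” at posttreatment, and “past week” at follow-up assessments".
- **Timing of the interview (Procedures).** "Participants will be recruited by a member of the research staff on the day following their inpatient admission or later". Those who "agree to participate will provide written informed consent prior to any study procedures". Only then: "Enrolled participants will undergo a clinical assessment by an independent evaluator (IE), who will administer the DIAMOND, C-SSRS, SIGH-D, and IAT".

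The C-SSRS gives ideation and behaviour severity scores, each 0 to 5, and "suicidal behavior can also be scored dichotomously (present/absent"). The Analytic Plan lists effect sizes for both severity scores, from pre-treatment through follow-up, as outcomes 5 and 6.

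**The concern.** The baseline sentence treats admission and pre-treatment as one time point. The Procedures section makes them different days, with no upper limit on the distance between them. No text says whether the baseline week ends at the hospital admission or at the interview, and no text says that the qualifying attempt must be scored at baseline.

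Two things are at stake. Everyone enrolled has recently attempted suicide, yet a participant could have that attempt left out of the baseline behaviour score, and ideation around the attempt could be left out with it. Separately, ideation or behaviour that occurred in hospital before the first CBT session could be scored as a post-treatment result. Both bear on outcomes 5 and 6, which the Analytic Plan ranks above its significance tests and which are meant to inform a grant proposal for a randomized trial.

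**Working it through.** The plan gives no figure on this point, so there is nothing to reproduce. The check is window arithmetic.

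**Inputs from the documents**

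- Eligibility look-back: 7 days before admission as defined in criterion 4.
- Baseline look-back: 7 days (Measures).
- Interview: at least 1 day after inpatient admission (Procedures).
- Sample: 5 to 10 patients, one arm (Participants).

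**Not in the documents, so assumed:** the distribution of the attempt-to-admission gap, the length of any medical-floor stay, and the recruitment lag beyond its one-day minimum.

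**Step 1. When is the attempt missed?** Let L be the days from attempt to eligibility admission (0 to 7). Let G be the days from that admission to the interview, that is, medical stay plus recruitment lag, so G is at least 1. The attempt lies L + G days before the interview. A past week counted from the interview misses it when L + G > 7, or L > 7 − G. The oldest eligible attempt lies 7 + G days back, at least 8 days against a 7-day window. G = 1 misses L > 6, G = 3 misses L > 4, and G = 5 misses L > 2.

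**Step 2. What share would be missed?**

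- L spread evenly over 0 to 7 days: share = G/7.
- L exponential with mean m, cut at 7 days: share = [exp(−(7−G)/m) − exp(−7/m)] / [1 − exp(−7/m)]. For m = 1 and G = 1 this is (0.00248 − 0.00091)/0.99909 = 0.0016.

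| G (days) | Medical stay with 1-day lag | Even spread | Exponential, mean 2 days | Exponential, mean 1 day |
|---|---|---|---|---|
| 1 | 0 | 14% | 2.0% | 0.2% |
| 3 | 2 | 43% | 10.8% | 1.7% |
| 4 | 3 | 57% | 19.9% | 4.9% |
| 6 | 5 | 86% | 59.4% | 37% |

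Each row applies only to patients with that G, not to the whole sample.

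**Step 3. What does that mean for 10 patients?** The chance of at least one miss is 1 − (1 − p)^10 if all share the same G. At G = 1 it is 1 − (6/7)^10 = 79% (even spread), 18.5% (mean 2 days) or 1.6% (mean 1 day). At G = 3 it is 99.6%, 68% or 16%. One missed patient is 1/10 to 1/5 of the sample, or 10% to 20%.

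**Step 4. Compare the possible readings of admission in the Measures sentence.**

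| Reading | Baseline window | Post-treatment window | Result |
|---|---|---|---|
| Hospital date for both | 7 days before admission | From hospital admission | Attempt captured if admission is as in criterion 4; G days before the interview count as post-treatment |
| Interview for baseline, hospital date for post-treatment | 7 days before interview | From hospital admission | Attempt can be missed; days between admission and interview can count at both time points |
| Visit label for both | 7 days before interview | From baseline interview | No overlap; attempt can be missed |

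No reading is free of a fault.

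**The case against.** The strongest reply is that the Measures sentence pairs a week at admission with a period since admission, so the two windows meet at the hospital date. Baseline then covers the same week as criterion 4 and nothing is missed. This is a fair reading, and it makes the missed-attempt problem conditional. It does not clear the plan, because the post-treatment window then includes at least one day before any CBT. Nor is it the only fair reading: the follow-up past week can only be counted from the interview, and the Budget section uses admission as the name of an assessment point. If admission is a visit label throughout, the overlap goes but the attempt can be missed.

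Four further objections stand as limits.

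- **Frequency.** A reader might infer from the 43% and 57% figures that many attempts will be missed. The documents do not support that. Those figures assume evenly spread gaps together with a 2- or 3-day medical stay, and patients who need stabilization may be admitted soon after the attempt.
- **Direction.** A reader might infer that the trial would overstate benefit. A missed attempt can only lower baseline or leave it unchanged, so it understates improvement.
- **Score.** Baseline behaviour is scored absent only if no other suicidal behaviour falls in the window. The attempt is still known from eligibility screening and from the therapist's assessment in CBT phase I.
- **Length.** A reader might infer that baseline would cover a different length of time in each patient. A past week counted from the interview is 7 days for everyone, as at follow-up. Only its position relative to the attempt varies.

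**Conclusion.** The point holds as an inconsistency of anchors that should be corrected. Counted from the interview, the baseline week can exclude an eligible attempt, since the oldest one lies at least 8 days back. Counted from the hospital date, baseline is sound, but the post-treatment score takes in G days (at least 1) of pre-CBT time. If severity is scored as the worst level in the window, those extra days can only raise the post-treatment score or leave it unchanged, which again understates improvement.

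The size is not known. With a one-day lag and medical stays of 0 to 3 days, the share missed is between 0.2% and 57%, depending wholly on assumed timing, and it rises with longer stays. If admission follows the attempt quickly and the interview is the next day, misses will be rare. With 5 to 10 patients a single case still carries weight. The documents show that the fault can occur, not that it will be common.

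**What to change.** In Measures:

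1. Define the baseline C-SSRS window, for ideation and behaviour, as the fixed 7 days ending at first hospital admission as defined in inclusion criterion 4. Every qualifying attempt is then captured by construction, and the length matches the 7-day follow-up windows.
2. Record ideation and behaviour between that admission and the baseline interview separately, as pre-treatment.
3. Start the post-treatment window at the baseline interview instead of at admission.
4. Record the dates of attempt, admission and interview.

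Stretching the baseline window to run up to the interview is not advised. It would last 7 + G days (8 at minimum, 11 with a 3-day stay and one-day lag), would differ between patients, and would always exceed the follow-up window. A longer look-back could then exaggerate the reduction.

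The cost is a few sentences and an instruction to the evaluator. There are two downsides. Recall at baseline reaches back 7 + G days instead of 7. And because every patient then has an attempt at baseline by eligibility, the report should say that the fall in behaviour score is partly built in by selection.

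### The follow-up C-SSRS interview asks about only some 21 of 91 post-discharge days, and no listed outcome counts participants with suicidal behavior or an attempt through month 3

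*Combined protocol and SAP*

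**What the plan says.** All references are to the combined protocol and SAP.

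- **Recall window.** Measures gives the C-SSRS a past-week timeframe at pre-treatment, then "and “since admission” at posttreatment, and “past week” at follow-up assessments". It adds that "suicidal behavior can also be scored dichotomously (present/absent" is an available scoring.
- **Schedule.** The follow-up paragraph (just before Adverse Event reporting) states: "After discharge, participants will have a telephone interview at 1 month, 2 month, and 3 month follow-up". The C-SSRS is the only instrument named for these calls. The preceding C-SSRS is given "after the 10th session or within 24 hrs. prior to discharge, whichever comes first".
- **Chart review.** The same paragraph says: "Data retrieved at 1, 2, and 3-month post-discharge will include readmission rates to the IOL or ED". It continues: "Whether suicide attempt preceded admission will also be recorded".
- **Outcomes.** Analytic Plan outcome 6 is the Hedges's g "of C-SSRS behavior severity score from pre-treatment through follow-up". Outcome 8 compares enrolled with eligible but unrecruited patients on readmission. None of the eight outcomes is a count of participants with an attempt or with any suicidal behavior.
- **Purpose.** Method says the treatment was chosen because its outpatient trial "resulted in a significant reduction in suicide attempts over a 24-month follow-up assessment (hazard ratio = 0.38". The Rationale stresses the 90 days after hospitalization. Aim 2 includes pilot efficacy data, and Future Plans uses them to support a proposal for a randomized trial.

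**The concern.** A past-week window suits ideation, which can be read as a current state. Suicidal behavior is a set of discrete events, so a seven-day window once a month only samples it. The interview leaves three stretches of about 23 days each unasked, and the first starts at discharge. A patient interviewed after session 10 who then stays in hospital has further unasked inpatient days.

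At stake is a simple descriptive figure: how many of the 5–10 participants attempted suicide, or had any suicidal behavior, between the post-treatment interview and month 3. With so few participants, one unrecorded attempter is 10 to 20 percentage points (1/10 to 1/5). Every participant enters with a recent attempt. If the three past-week ratings were read as a record of the whole follow-up, missed events would make follow-up look better than it was. Days not asked about cannot be reliably reconstructed later.

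**Working it through.** **Inputs from the documents:** three calls, at 1, 2 and 3 months; a seven-day window at each; 5–10 participants. The plan gives no day count for follow-up and no coverage figure, so there is nothing of its own to reproduce. I take 3 × 30.44 = 91.3 days and vary it.

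**Day count**
- Asked about: 3 × 7 = 21 days. 21/91.3 = 23.0%.
- Not asked about: 91.3 − 21 = 70.3 days (77%).
- Each gap: 30.44 − 7 = 23.4 days.
- Other lengths: 21/84 = 25.0%; 21/90 = 23.3%; 21/93 = 22.6%. If past week is read as 8 days, 24/91 = 26.4%.
- One missed call: 14/91.3 = 15.3%.

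**Illustration.** The following are assumptions, not document figures: attempt risk p to month 3, one attempt per attempter, even timing, and a share c of the attempts outside the windows that chart review catches.

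- Share of attempts recorded by either source: d = 0.23 + 0.77c.
- Chance that no attempt is recorded: (1 − p·d)^n.

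For p = 0.20:

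| Source | d | n = 10 | n = 5 |
|---|---|---|---|
| C-SSRS alone (c = 0) | 0.230 | 0.954^10 = 62% | 79% |
| plus chart review, c = 0.25 | 0.4225 | 0.9155^10 = 41% | 64% |
| plus chart review, c = 0.50 | 0.615 | 0.877^10 = 27% | 52% |
| plus chart review, c = 0.75 | 0.8075 | 0.8385^10 = 17% | 41% |
| full coverage | 1 | 0.8^10 = 11% | 33% |

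Expected attempters recorded at n = 10 (n·p·d): 0.46 from the C-SSRS alone; 0.84, 1.23 and 1.61 with chart review at the three values of c; 2.0 with full coverage.

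Other risks at n = 10, same formula:
- p = 0.10: 0.95775^10 = 65% (c = 0.25) to 0.91925^10 = 43% (c = 0.75), against 35% with full coverage.
- p = 0.30: 0.87325^10 = 26% to 0.75775^10 = 6%, against 3%.

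**Timing.** If the event rate declines exponentially after discharge with a half-life of 60, 30 or 15 days (assumed), the three windows contain 20.0%, 17.2% or 12.4% of attempts instead of 23%. The chance that the C-SSRS alone records none (p = 0.20, n = 10) moves from 0.624 to 0.665, 0.705 or 0.778. Even timing is therefore the milder assumption.

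**The case against.** **Chart review already covers attempts.** A reader might infer from the day count that attempts on the other 70 days go unrecorded. The documents do not support that. Chart review is not confined to the three weeks, and it notes whether an attempt preceded an admission. This stands, and it is why the 62% for the C-SSRS alone is not the plan's expected performance. The remainder is real, though. Attempts without an IOL or ED visit, and behavior short of an attempt, are not said to be captured. Nor is the attempt flag said to feed outcome 6 or any other listed outcome.

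**The past-week window has a purpose.** It matches the pre-treatment window, so the follow-up g for behavior against baseline compares like with like. This also stands, and a reader should not conclude that this contrast is biased by the gaps. The exception is the post-treatment point, whose since-admission window differs from the baseline week.

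**The study is too small for this to matter.** Five to ten patients in a single group cannot yield anything comparable with a 24-month randomized hazard ratio, and the plan says it is not powered. I agree that the attempt figure stays imprecise even with full coverage. But an imprecise complete count is more useful than one that is both imprecise and incomplete. Whether whole-period behavior can be collected by telephone is itself a feasibility question for the later trial.

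**The since-admission wording.** One might read it as meaning since the pre-treatment interview and want it rewritten. Participants defines admission expressly as admission to the medical floor or the IOL, so I propose no change there.

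**Conclusion.** The concern holds as a limit on what the pilot can report. It is not a fault in the planned effect sizes at follow-up. The C-SSRS interview covers about 23% of the three months after discharge (23–25% across reasonable lengths). Chart review adds an unknown part of the rest, and no listed outcome says how many participants had suicidal behavior or an attempt over that period.

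Only the day count rests on the documents, together with an assumed length of about 91 days. The probabilities depend on assumed risk, timing and chart-review capture. At 20% risk and 10 participants, the chance of recording no attempt from either source is 41% to 17%, against 11% with full coverage. The Rationale's 90-day figures concern suicide deaths; I use them only to show which period the authors consider important. I class this as a cheap improvement, best made before calls begin.

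**What to change.** **Measures.** Keep the past-week window for ideation and for the Hedges's g on behavior. At each of the three planned calls, add the C-SSRS behavior items for the period since the last completed C-SSRS assessment. At month 1 this also takes in any inpatient days after a session-10 interview.

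**Analytic Plan.** Add one descriptive outcome: the number and percent of participants with any suicidal behavior, and with any attempt (present/absent), from the post-treatment interview to month 3. List chart-review attempts beside it, and state how many participants have incomplete interview coverage.

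**Limits.** With all calls completed, interview coverage rises from 21 of 91 days to all 91. A missed call is made good only for participants who complete a later one. Those withdrawn under the rule for participants who cannot be reached (three call attempts, then two letters) stay uncovered except by chart review.

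**Cost.** Two or three sentences of text and one extra behavior question set at calls already scheduled, with no added visits, calls or staff. The price is about one month of recall, longer after a missed call. The longer window must not be used for g against the seven-day baseline.
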